3.3.1 Selection of Study Dose

Standard treatment regimens with currently approved IS therapies involve achieving high maintenance dose levels rapidly⁴⁹. For example, VGB is initially given at a dose of 50 mg/kg/day and can be titrated by 25–50 mg/kg/day increments every 3 days to a maximum dose of 150 mg/kg/day⁵⁰; both of these doses are approximately 3 times the recommended initial and maximal dose of VGB in adults. Moreover, treatment with ACTH, which is injected intramuscularly, begins at the maintenance dose immediately (150 IU/m²/day recommended)⁵¹. Consequently, due to the urgency required in achieving efficacious doses to treat this population, rapid titration to a maximal safe and tolerable maintenance dose is proposed in this trial in infants with IS. The titration regimen proposed for use on this trial was discussed, and agreed, with consultants. Due to the rapid titration of the IMP, all patients in the pilot phase will be inpatient during the 4-day titration period. Following independent data safety monitoring committee (DSMC) review, adjustment of doses and dose regimens may occur during the trial, as well as plans for the dose titration during the pivotal phase.

The DSMCs of the GW studies in Dravet syndrome patients (GWEP1332, GWEP1424) and LGS patients (GWEP1414, GWEP1423) recommended a target of 20 mg/kg/day as a safe and tolerable dose during a 14-week treatment period. The lower age limit in these studies is 2 years of age. Three of the 4 studies are now complete; preliminary data from the GWEP1332 trial show GWP42003-P was generally well tolerated. The most common AEs (occurring in greater than 10% of GWP42003-P-treated patients [n=61]) were: somnolence, diarrhea, decreased appetite, fatigue, pyrexia, vomiting, lethargy, upper respiratory tract infection and convulsion. Of those patients on GWP42003-P for whom an AE was reported, 84% of these AEs were mild or moderate.

Data on the safety of GWP42003-P is also emerging from the physician-initiated EAP being conducted in the US as well as other compassionate use worldwide. This program has been running since January 2014 and, at the time of writing, has now exposed 693 patients to CBD oral solution. The last data cut (September 2015) shows that the mean maximum exposure achieved in this patient population of refractory epilepsies was a daily dose of approximately 25 mg/kg CBD with a maximum dose of 51 mg/kg in 1 patient. Among the 350 patients in the safety data set, 47% were taking > 20 and ≤ 30 mg/kg/day CBD and 18% taking > 30 and ≤ 50 mg/kg/day CBD. In healthy adults administered doses of up to 1500 mg GWP42003-P twice daily for

EudraCT Number: 2015-004904-50

Protocol V3 20Sep16

6 consecutive days with a single morning dose on Day 7, treatment emergent adverse events (TEAEs) reported in 95.8% of all subjects were of mild or moderate severity. The twice daily dose of 1500 mg equates to 40 mg/kg/day in a 75 kg adult. In addition, 75.0% of subjects administered single doses of up to 6000 mg CBD (equivalent to 80 mg/kg in a 75 kg adult) reported TEAEs, all of mild or moderate severity. When 1500 mg GWP42003-P was administered to subjects alongside a high fat breakfast, a 4.85-fold increase in the maximum measured plasma concentration and a 4.20-fold increase in exposure (measured as area under the concentration-time curve calculated to the last observable concentration at time t) for CBD were observed. The extent of the food effect was also reflected in CBD metabolite exposure. The exposure increase coincided with a higher incidence, but no increased severity, of TEAEs in the fed compared to the fasted group ⁵².

In view of the higher metabolic rate of children aged up to 2 years, it has been recommended by consultants that dosing should be approximately 30–40% higher than that used for patients 2 years and older. To reflect this, and in light of the emerging RCT and EAP data detailed above, a target dose of 40 mg/kg/day is proposed in this trial in infants with IS.

3.4 Clinical Hypothesis

The primary clinical hypothesis is that there will be a difference between GWP42003-P and placebo during the pivotal phase in their effect on IS, as measured by elimination of clinical spasms and hypsarrhythmia.

This trial will also evaluate the effect of GWP42003-P compared with placebo on time to cessation of clinical spasms and changes in other seizure types. The safety and tolerability of GWP42003-P will also be assessed during the pilot phase, pivotal phase (compared with placebo) and OLE phase of the trial.

EudraCT Number: 2015-004904-50

Protocol V3 20Sep16

4 EXPERIMENTAL PLAN

4.1 Trial Design

This is a multisite trial to evaluate the efficacy and safety of GWP42003-P in patients with IS who have failed to become spasm- and hypsarrhythmia-free following treatment with 1 or more approved IS therapies (e.g., steroids and/or VGB). All approved therapies must be discussed with the patient's parent(s)/legal representative before the patient is considered for the trial (discussions regarding treatment options must be documented). The trial will comprise of a pilot safety phase, followed by a pivotal phase, with a 1 year open-label extension available to all patients who complete either phase. The pilot phase will be open-label with 2 sequential cohorts of 5 patients, the first cohort aged between 6 and 24 months and the second cohort aged between 1 and 24 months, who will receive GWP42003-P for 2 weeks. The pivotal phase will comprise 192 patients, aged 1–24 months, who will undergo a 2-week, randomized, placebo-controlled, double-blind treatment period.

An independent DSMC will be used throughout the study; they will consider safety of the patients, and will confirm doses and dose regimens to be investigated in the pivotal phase, as well as the plans for dose titration. If required, following DSMC review, adjustment of doses and dose regimens will also take place following the first cohort of 5 patients in the pilot phase.

Patients will enter the pilot and pivotal phases at the respective screening visits (Visit 1, Day -7 to -1) for assessment of eligibility, which includes a prolonged video-EEG. Patients who satisfy all eligibility criteria will then be administered GWP42003-P (pilot phase) or randomized to GWP42003-P (1 of 2 dose levels) or placebo at a 1:1:1 ratio (pivotal phase) (Visit 2, Day 1 [+3 days]). The High Dose Level will be as recommended by the DSMC; the Low Dose Level will be defined as 50% of the High Dose Level. Patients in the placebo group will be split into 2 equivalent cohorts: half receiving Low Dose Level dosing volumes and half receiving High Dose Level dosing volumes. Following baseline assessments, patients will titrate the IMP in 10 mg/kg/day increments to the target dose level (or equivalent volume of placebo in the pivotal phase) and will continue at this dose, or the highest tolerated dose up to 40 mg/kg/day, for the remainder of the 2-week treatment phase. Patients in the pilot phase will remain in the clinic as inpatients during the 4-day dose titration period. If deemed safe by the DSMC then it is planned for those in the pivotal phase to titrate in an outpatient setting. Further clinic-based assessments will take place after 3 days' dosing (Visit 3, Day 4 [+1 day]). All patients in the pilot and pivotal phases will return to the clinic after 2 weeks' dosing (Visit 4, Day 15 [+3 days]) or earlier if they withdraw prematurely. All patients who complete

EudraCT Number: 2015-004904-50

Protocol V3 20Sep16

treatment will then have the opportunity to receive GWP42003-P during the subsequent OLE phase. The OLE phase will last for a maximum of 1 year.

Patients who enter the OLE phase will remain on the same dose (pilot phase) or will transition to their target dose of GWP42003-P over 4 days in a blinded manner (pivotal phase). Patients may continue at this dose, or the highest tolerated dose up to 40 mg/kg/day, for the remainder of the OLE phase. GWP42003-P may be discontinued at the discretion of the investigator (Section 9.1.2). During the OLE phase, clinic visits will take place on Day 19 (Visit 5 [+1 day]), Day 29 (Visit 6 [±3 days]), Day 43 (Visit 7 [±3 days]), Day 71 (Visit 8 [±3 days]), Day 127 (Visit 9 [±7 days]), Day 211 (Visit 10 [±7 days]), and on Day 295 (Visit 11 [±7 days]). Patients will return to the site for an end of OLE treatment visit on Day 379 (Visit 12 [±7 days]) or earlier if they withdraw prematurely from the OLE phase. Following end of treatment, withdrawal, or discontinuation of IMP, all patients will taper the IMP over 10 days followed by safety follow-up. Patient diaries will be completed each day by the caregiver during the trial.

A series of schematic diagrams (Figure 1-1, Figure 1-2, and Figure 1-3), presented at the end of Section 1, depict the overall trial design. More detailed information on treatment and trial procedures is provided in Section 8 and Section 9, respectively.

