satisfy all eligibility criteria will then be administered GWP42003-P (pilot phase) or randomized to GWP42003-P (1 of 2 dose levels) or placebo at a 1:1:1 ratio (pivotal phase) (Visit 2, Day 1 [+3 days]). The High Dose Level will be as recommended by the DSMC; the Low Dose Level will be defined as 50% of the High Dose Level. Patients in the placebo group will be split into 2 equivalent cohorts: half receiving Low Dose Level dosing volumes and half receiving High Dose Level dosing volumes. Following baseline assessments, patients will titrate the investigational medicinal product (IMP) in 10 mg/kg/day increments to the target dose level (or equivalent volume of placebo in the pivotal phase) and will continue at this dose, or the highest tolerated dose up to a maximum of 40 mg/kg/day, for the remainder of the 2-week treatment phase. Patients in the pilot phase will remain in the clinic as inpatients during the 4-day titration period. If deemed safe by the DSMC, then it is planned for those in the pivotal phase to titrate in an outpatient setting. Further clinic-based assessments will take place after 3 days' dosing (Visit 3, Day 4 [+1 day]). All patients in the pilot and pivotal phases will return to the clinic after 2 weeks of dosing (Visit 4, Day 15 [+3 days]) or earlier if they withdraw prematurely. All patients who complete treatment will then have the opportunity to receive GWP42003-P during the subsequent OLE phase. The OLE phase will last for a maximum of 1 year. Patients who enter the OLE phase will remain on the same dose (pilot phase) or will transition to their target dose of GWP42003-P over 4 days in a blinded manner (pivotal phase). Patients may continue at this dose, or the highest tolerated dose up to a maximum of 40 mg/kg/day, for the remainder of the OLE phase. GWP42003-P may be discontinued at the discretion of the investigator. During the OLE phase, clinic visits will take place on Day 19 (Visit 5 [+1 day]), Day 29 (Visit 6 [±3 days]), Day 43 (Visit 7 [±3 days]), Day 71 (Visit 8 [±3 days]), Day 127 (Visit 9 $[\pm 7 \text{ days}]$), Day 211 (Visit 10 $[\pm 7 \text{ days}]$), and on Day 295 (Visit 11 [\pm 7 days]). Patients will return to the site for an end of OLE treatment visit on Day 379 (Visit 12 [±7 days]) or earlier if they withdraw prematurely from the OLE phase. Following end of treatment, withdrawal, or discontinuation of IMP, all patients will taper the IMP over 10 days followed by

Primary Endpoint

Pilot Phase:

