Investigational Medicinal Product:	Dose (pivotal phase): Patients will titrate the IMP to the target dose level over 4 days and will continue at this dose, or the highest tolerated dose up to the target dose level, for the remainder of the blinded treatment phase.
Formulation, Mode of Administration, Dose and Regimen (continued)	Dose (OLE phase): Patients will remain on the same dose (pilot phase) or will transition to the target dose of GWP42003-P, or the highest tolerated dose up to 40 mg/kg/day, over 4 days (10 mg/kg/day), in a blinded manner (pivotal phase). Patients may continue at this dose for the remainder of the OLE phase. GWP42003-P may be discontinued at any time during the OLE phase, at the discretion of the investigator, but patients who have become spasm-free and have resolution of hypsarrhythmia will be encouraged to continue to attend all subsequent clinic visits. Dosage: IMP is taken twice daily (morning and evening), maintaining consistency with regard to feeds/meals and other concomitant medications, and can be taken with other concomitant medications as directed by the investigator. In the event that the IMP is poorly tolerated, dosing may be changed to 3 times daily (while keeping the equivalent total daily dose), following approval by the GW medical monitor. The recommended dosing intervals are:
	 12-hourly (8-hourly minimum) for twice daily dosing. 6-hourly (minimum) for 3 times daily dosing.
Control Group	The control group in the pivotal phase will receive equivalent dosing volumes of matching placebo.
Procedures	Pilot and Pivotal Phase
	Visit 1 (Day -7 to Day -1): Screening
	The following will be collected/assessed:
	Informed consent.
	Eligibility criteria.
	Patient demographics.
	Full medical history.
	Concomitant medication review.
	• Physical examination (including length [height], body weight, and head circumference).
	• Vital signs (including supine blood pressure).
	• ECG.
	• Video-EEG (8–24 hours in duration).
	• Clinical laboratory samples (blood and urine [if possible]) for:
	 Serum biochemistry.
	- Hematology.

EudraCT Number: 2015-004904-50

Protocol V3 20Sep16

Urinalysis.

Procedures (continued)

To minimize the volume of blood required, serum biochemistry and hematology results from samples analyzed up to 3 days prior to Visit 1 may be used.

- AEs.

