8.1.2 Dose Escalation and Dose Adjustments

All patients will be weighed during each clinic visit where IMP is dispensed (i.e., no physical exam performed at Visit 3 [Day 4] or Visit 5 [Day 19]). The volumes of IMP solution to be taken each day during the titration periods, and for the remainder of each phase of the trial, will be calculated and provided to the patient's caregiver. If an unacceptable AE develops at any time during the titration periods, dosing should initially be amended or suspended, at the investigator's discretion, until the event has resolved or is well tolerated. During the maintenance periods, patients should continue on a stable dosing regimen at the target dose. However, if the patient is not able to tolerate the target dose, the investigator may consider temporarily or permanently reducing the dose or dosage for the remainder of the maintenance period.

Eligible patients will be assigned GWP42003-P (pilot phase) or randomly allocated to GWP42003-P or matching placebo (pivotal phase) and will titrate the IMP over 4 days according to the titration regimen, an example titration regimen up to

EudraCT Number: 2015-004904-50

Protocol V3 20Sep16

40 mg/kg/day over 4 days is shown in Table 8.1.2-1. Patients in the pilot phase will remain in the clinic as inpatients during the 4-day titration period. If the DSMC confirms it is safe then patients in the pivotal phase will titrate the IMP as outpatients. For the pivotal phase there will be 2 dose levels; the High Dose Level will be as recommended by the DSMC, the Low Dose Level will be defined as 50% of the High Dose Level. Patients in the placebo group will be split into 2 equivalent cohorts: half receiving Low Dose Level dosing volumes and half receiving High Dose Level dosing volumes. In both phases, daily safety checks will be made during the first week of IMP dosing.

Table 8.1.2-1 Exam	ble 8.1.2-1 Example Titration Regimen: Pilot and Pivotal Phase					
Day	IMP Dosage	Total Daily IMP Dose ²				
1	5 mg/kg (am/pm)	10 mg/kg				
2	10 mg/kg (am/pm)	20 mg/kg				
3	15 mg/kg (am/pm)	30 mg/kg				
4 onwards	20 mg/kg (am/pm)	40 mg/kg				

¹Volumes of IMP to be taken each day will be calculated using the patient's weight and the required dose.

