9.1.1.2 Visit 2 (Day 1 [+3 Days])

This visit will occur up to 7 (+3) days after Visit 1 (screening). Patients who satisfy all eligibility criteria (Section 6) during the screening period will be assigned GWP42003-P (pilot phase) or randomly allocated to GWP42003-P or matching placebo (pivotal phase) using the IVRS/IWRS (Section 9.2.2). Eligible patients must begin treatment within 7 days of their video-EEG screening assessment. The following will be collected/assessed prior to the patient receiving IMP:

- Concomitant medication review (Section 9.2.5).
- Physical examination (Section 9.2.6).
- Vital signs (Section 9.2.7).
- CGIC memory aid (Section 9.2.12.1).
- PGIC memory aid (Section 9.2.12.2).
- Vineland-II (Section 9.2.12.3).
- Caregiver diary review (Section 9.2.13) for:
 - Spasm/seizure information.
 - Changes in concomitant AEDs.
 - Usage of rescue medication.
 - AEs.
- AEs (Section 12).

Patients will receive sufficient IMP for 2 weeks of dosing. Patients in the pilot phase will remain in the clinic as inpatients during the 4-day titration period. For all patients, the first dose of IMP will be taken in the clinic on the morning of Day 1 with

EudraCT Number: 2015-004904-50

Protocol V3 20Sep16

an ECG assessment between 3 and 5 hours postdose (Section 9.2.8). For patients involved in the pivotal phase of the trial, a PK blood sample will be taken, provided the risk/benefit outcome is favorable in the investigator's opinion (Section 9.2.11). If a PK blood sample is collected, the investigator must note the sampling time and the dosing times of IMP and of any concomitant AEDs taken that day and the previous day. Patients will titrate to their target dose of GWP42003-P (or equivalent volume of placebo in the pivotal phase; Section 8.1.2) and will continue at this dose, or the highest tolerated dose up to 40 mg/kg/day, for the remainder of the 2-week treatment phase. During this time, the patient's current IS therapy may be continued or tapered, at the discretion of the investigator. All non-pharmacological interventions for epilepsy (including ketogenic diet and any neurostimulation devices for epilepsy) must remain stable during the pilot and pivotal phases of the trial. Following Visit 2, daily safety checks will be made during the first week of IMP dosing.

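### The pivotal-phase dose ceiling is stated inconsistently: the assigned target dose level in one place, a fixed 40 mg/kg/day in four others

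*Protocol*

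**What the plan says.** Two forms of ceiling appear for the blinded two-week treatment period.

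- **Assigned target.** The synopsis dose entry for the pivotal phase lets patients stay at target "or the highest tolerated dose up to the target dose level, for the remainder of the blinded treatment phase".
- **Fixed figure.** Section 4.1 says patients "will continue at this dose, or the highest tolerated dose up to 40 mg/kg/day, for the remainder of the 2-week treatment phase". The synopsis Trial Design entry has "or the highest tolerated dose up to a maximum of 40 mg/kg/day, for the remainder of the 2-week treatment phase", Section 9.1.1.2 has "or the highest tolerated dose up to 40 mg/kg/day, for the remainder of the 2-week treatment phase", and SAP Section 2.1 repeats the Section 4.1 sentence.

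The fixed figure is not confined to the pilot. In Section 4.1 the same sentence has patients titrating "to the target dose level (or equivalent volume of placebo in the pivotal phase"), and the other three places also name the pivotal phase in that sentence.

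Section 8.1.2, the dosing section, keeps patients at target during maintenance and speaks only of going down: "if the patient is not able to tolerate the target dose, the investigator may consider temporarily or permanently reducing the dose or dosage". The footnote to its titration tables likewise mentions only a lower dose.

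The protocol gives no number for the pivotal levels. Section 4.1 leaves the High Dose Level to the DSMC's recommendation, and "the Low Dose Level will be defined as 50% of the High Dose Level".

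**The concern.** A dose ceiling is a limit that sites act on. Here the patients are infants aged 1 to 24 months, and about 50 sites are expected. The same pivotal patient has one ceiling in the synopsis dose entry and another in the Visit 2 procedures.

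Two things are at stake. The first is arm separation. The primary analysis compares each dose level with placebo, which presumes that a Low Dose patient is treated at or below the Low Dose Level. A ceiling printed above that level could be taken to permit more. The second is the link to the DSMC. The committee is to confirm the pivotal doses after the pilot, and a figure fixed in the text does not move if it recommends less than 40 mg/kg/day.

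**Working it through.** **Origin of the 40.** It is the pilot target in the synopsis and the end of the example titration in Table 8.1.2-1. Four daily steps of 10 mg/kg/day give 10, 20, 30 and 40, which matches the table. For the pilot, target and fixed ceiling coincide and there is no conflict.

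**Pivotal inputs.** Let H be the High Dose Level in mg/kg/day (set by the DSMC, no value given). The Low Dose Level is 0.5 × H (Section 4.1). The fixed ceiling is 40.

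**Formulas.** Ratio of the fixed ceiling to the High target = 40 / H. Ratio to the Low target = 40 / (0.5 × H) = 80 / H.

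Every H below is an assumption, used to show the range.

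| Assumed H | High target | Low target | 40 / High target | 40 / Low target |
|---|---|---|---|---|
| 40 | 40 | 20 | 1.0 | 2.0 |
| 30 | 30 | 15 | 1.33 | 2.67 |
| 20 | 20 | 10 | 2.0 | 4.0 |

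The fixed ceiling equals a target in one cell only: the High arm at H = 40. For the Low arm it is above target at every H up to 40. For the High arm it is above target whenever H is below 40.

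**Which text governs.** Section 4.1 closes by sending the reader to Sections 8 and 9 for treatment and procedures. Those two do not settle the matter: Section 8.1.2 describes target or lower, while Section 9.1.1.2 prints 40 in a sentence that itself cites Section 8.1.2. No passage says which prevails.

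**Reach in the planned trial.** At 1:1:1, 192 / 3 = 64 patients per group. The Low arm's 64 would have had two different ceilings at any H up to 40, and the High arm's 64 also if H were below 40.

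**The case against.** The strongest reply is that the fixed wording does no harm when read in context. Patients titrate to the target dose level and continue there; the highest tolerated dose is then the fallback for those who cannot manage target. Section 8.1.2 supports this, and no passage describes raising a blinded patient above the assigned target. If H is 40 or less, a patient at or below target also satisfies a limit of 40, so both statements can be obeyed at once.

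Most of this stands, and it rules out several stronger readings.

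- A reader might infer that the protocol allows Low Dose patients to be taken to the High Dose Level. The documents describe no such step. In addition, 40 would be the High Dose Level only if H = 40.
- A reader might infer that the fixed figure overrides the DSMC. It does not: both arm targets follow the committee's recommendation, and only the printed outer limit would be out of date.
- A reader might try to estimate how far the arms would converge. That needs the fraction of Low patients dosed above target, and the documents give no basis for one.
- A reader might extend the point to the open-label extension. There the ceiling is consistently 40: "Patients may continue at this dose, or the highest tolerated dose up to 40 mg/kg/day, for the remainder of the OLE phase". There is no contradiction in it to reconcile.

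The reply does not remove the inconsistency. As a limit on a fallback dose, 40 does nothing for a Low Dose patient whose target is at most 20 when H is at most 40. The synopsis also separates the phases, giving 40 for the pilot and the target dose level for the pivotal phase, while the other four places apply one number to both.

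**Conclusion.** The point holds as an inconsistency in the stated pivotal-phase ceiling. The fixed 40 mg/kg/day is 2.0 times the Low target if H = 40, and 2.67 times Low and 1.33 times High if H = 30; both values of H are assumptions. Read literally, it could be taken to permit dosing above the assigned level, and it does not track a DSMC recommendation below 40.

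The realised consequence is nil for pivotal data: SAP Section 5 states that only patients from the open-label pilot were included and that the pivotal analyses were omitted. That limits the harm but does not correct the text, and SAP Section 2.1 still carries the fixed figure for the pivotal phase. A dose limit in infants that depends on which section a site reads should be resolved before any pivotal patient is dosed under this protocol. The documents do not settle which ceiling is intended, and nothing here chooses between them.

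**What to change.** Reconcile the synopsis Trial Design entry, the synopsis dose entry for the pivotal phase, Protocol Sections 4.1, 8.1.2 and 9.1.1.2, and SAP Section 2.1, so that the pivotal phase has one consistently stated ceiling. Which ceiling applies, and in what form it is written, is for the sponsor and the DSMC to decide.

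The cost is a wording change in a protocol amendment, a matching line in the SAP's design summary, and a check that any dosing instructions given to sites agree with the reconciled text. It needs no extra patients, visits or procedures and changes no planned analysis.
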